8.2 Setting and Study Population

8.2.1 Study Period

Study enrollment for Study 20130193 began in 2017. The study period will end after the last patient enrolled has had the opportunity to contribute 5 years of observation from the first dose of IMLYGIC.

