8.7 Data Analysis

8.7.1 Planned Analyses

8.7.1.1 Interim Analyses

During data collection, annual study progress reports will be completed for inclusion in Periodic Safety Update Reports. These interim analyses will report on study recruitment (eg, number of patients enrolled), study conduct (eg, patient-years of observation), and

Page 26 of 62

^d Assumes patient survival of 3 years, plus 15% more patients for additional loss to follow-up.

the primary and secondary endpoints assessed at that point in time. Additional ad hoc analysis may be conducted if required for submission to regulatory authorities.

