8.7.2 Planned Method of Analysis

8.7.2.1 General Considerations

This study is descriptive in nature and no formal hypothesis will be tested. Select summaries will also be presented **by** region.

This study will estimate incidence rate of herpetic infection. The incidence rate will be calculated as the number of events divided by sum of follow-up time in patient-years.

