IMLYGIC dose). If patients receive IMLYGIC over multiple treatment phases, the treatment period is defined as the sum of time from the date of first IMLYGIC dose to 30 days after the date of last IMLYGIC dose or the day before the subsequent treatment phase, whichever comes first, in each treatment phase in patient-years. As a measure of precision, a 95% confidence interval will be calculated around the incidence rate.

 Incidence rate of herpetic infection with detection of wild-type HSV-1 among patients after discontinuation of IMLYGIC

The incidence rate will be calculated as the number of suspected herpetic infections that test positive for wild-type HSV-1 divided by sum of follow-up time (last date of follow-up minus the date of last IMLYGIC dose plus 31 days). If patients receive IMLYGIC over multiple treatment phases, each post-treatment period is defined as sum of time from 31 days after date of last IMLYGIC dose in the prior treatment phase to one day prior to the date of the first IMLYGIC dose in the subsequent treatment phase or the end of study in patient-years. As a measure of precision, a 95% confidence interval will be calculated around the incidence rate.

Summary of patient characteristics

Demographic and clinical characteristics will be summarized using categorical (n and %) and continuous statistics (n, mean, standard deviation, median, quartiles, minimum and maximum).

• Treatment patterns of anticancer therapy (eg, types and sequence)

The number, types, and order of treatments received will be reported.

Incidence of use of antiherpetic therapy

Patient incidence (n and %) of use of antiherpetic therapy will be reported.

 Incidence of adverse events and serious adverse events during treatment with IMLYGIC

Patient incidence (n and %) of adverse events and serious adverse events occurring between the date of first IMLYGIC dose and the date of last IMLYGIC dose plus 30 days will be reported. If patients receive IMLYGIC over multiple treatment phases, the adverse events and serious adverse events collection period is defined as the date of first IMLYGIC dose to 30 days after the date of last IMLYGIC dose or the day before the subsequent treatment phase, whichever comes first, in each treatment phase

 Incidence of adverse events and of serious adverse events related to IMLYGIC after the treatment period with IMLYGIC

Protocol Number: 20130193 Date: 12 October 2022

Page 30 of 62

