Patient incidence (n and %) of adverse events and serious adverse events occurring after the date of last IMLYGIC dose plus 31 days will be reported. If patients receive IMLYGIC over multiple treatment phases, the adverse events and serious adverse events collection period is defined as 31 days after date of last IMLYGIC dose in the prior treatment phase to one day prior to the date of the first IMLYGIC dose in the subsequent treatment phase or the end of study.

Overall survival

Overall survival will be estimated using the Kaplan-Meier method with the time to death being calculated from the date of the first IMLYGIC dose.

Patients who are alive or lost to follow-up at the time of the analysis will be censored.

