8.7.3 Analysis of Safety Endpoints/Outcomes

Details of the analyses of safety endpoints are outlined in Section 8.7.2.4.2.

The Medical Dictionary for Regulatory Activities (MedDRA) version 19.0 or later will be used to code all adverse events.

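### Post-treatment related adverse events are reported only as a crude percentage of patients, which will rise across the annual reports as exposure accrues even if the underlying rate is constant

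*Protocol*

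**What the plan says.** Protocol Section 8.7.2.4.2 assigns a measure to each secondary endpoint. For related adverse events after the treatment period it is "Patient incidence (n and %) of adverse events and serious adverse events occurring after the date of last IMLYGIC dose plus 31 days". For adverse events on treatment it is "Patient incidence (n and %) of adverse events and serious adverse events occurring between the date of first IMLYGIC dose" and 30 days past the last dose. Section 8.7.3 adds no other measure: "Details of the analyses of safety endpoints are outlined in Section 8.7.2.4.2".

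The herpetic-infection endpoints are handled differently. Section 8.7.2.1 states: "The incidence rate will be calculated as the number of events divided by sum of follow-up time in patient-years". Section 8.7.2.4.2 then defines person-time for the same two windows, on treatment and from 31 days after the last dose, including repeated treatment phases, and attaches a 95% confidence interval.

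On timing, Section 8.7.1.1 says: "During data collection, annual study progress reports will be completed for inclusion in Periodic Safety Update Reports". These reports cover "the primary and secondary endpoints assessed at that point in time", so they carry the adverse event percentages. They also give total patient-years, but as a study-conduct item and not as a denominator for adverse events. Section 8.2.1 says: "Study enrollment for Study 20130193 began in 2017". Section 8.2.5 ends a patient's follow-up at 5 years from first dose, death, withdrawal of consent or loss, whichever comes first.

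**The concern.** Time at risk in the post-treatment window runs from a few days to almost 5 years. At each annual cut, patients who are still on treatment, or have only just stopped, count in the percentage with little or no post-treatment time. As the cohort matures their time grows, and so does the share with an event, without any change in risk.

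Long-term safety in treated patients is part of the study title, and the post-treatment related-event endpoint is where the protocol addresses it. A reader of successive safety reports could take growing exposure for an emerging signal, or be reassured by a low early percentage. The protocol avoids this problem for herpetic infection but not for adverse events.

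**Working it through.** **The plan's own figures.** The protocol gives no expected adverse event incidence. Its only design figures (Section 8.5) are in person-time, and they reproduce: 1 − exp(−0.003 × 535) = 1 − exp(−1.605) = 0.799, the stated 80%; and with zero events the upper bound is 3.689/535 = 6.9 per 1000 patient-years.

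**Inputs from the protocol**
- Mean survival about 2 years (Section 8.5), taken as exponential: death rate 0.50 per year.
- Loss of 6% among the first 82 patients (Section 8.5). No time base is given, so 3% per year is assumed (0% to 8% tried). Total exit rate μ = 0.50 + 0.03 = 0.53.
- Median treatment about 6 months in the trial setting (Study Design Schema), taken as exponential with rate λ = ln 2/0.5 = 1.386. The post-treatment window opens d = 30/365.25 = 0.082 years after the last dose. One treatment phase is modelled.
- Follow-up capped at 5 years (Section 8.2.5).

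**Assumptions without a source in the protocol**
- Constant related-event hazard a = 0.05 per patient-year (0.01 and 0.20 as range).
- Uniform enrolment over 5 years.

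**Formula.** For a patient whose first dose was t years before the cut, with s = t − d > 0 and k = a + μ, the probability of a post-treatment event by the cut is

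F(t) = λ·e^(−μd)·(a/k)·{[1 − e^(−(λ+μ)s)]/(λ+μ) − e^(−ks)·[1 − e^(−(λ+μ−k)s)]/(λ+μ−k)}.

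At t = 5, s = 4.918 and k = 0.58, so F = 1.386 × 0.957 × 0.0862 × (0.5218 − 0.0431) = 0.0548.

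The crude percentage at year c is the mean of F over enrolled patients: t is uniform on [0, c] up to year 5, then on [c − 5, c] and capped at 5.

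| Years since first enrolment | Mean post-treatment years at risk per enrolled patient | Crude % | First events per patient-year |
|---|---|---|---|
| 1 | 0.101 | 0.5 | 0.05 |
| 3 | 0.448 | 2.2 | 0.05 |
| 5 | 0.672 | 3.4 | 0.05 |
| 7 | 0.996 | 5.0 | 0.05 |
| 10 | 1.095 | 5.5 | 0.05 |

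The crude percentage is simply hazard × mean time at risk (0.05 × 0.101 = 0.5%; 0.05 × 1.095 = 5.5%), so it rises because exposure rises. A simulation with annual cuts gave the same figures to within 0.1 percentage points.

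**Sensitivity, post-treatment endpoint (years 1, 5 and 10)**
- Hazard 0.01: 0.1%, 0.7%, 1.2%. Hazard 0.20: 2.0%, 11.7%, 18.1%.
- Accelerating enrolment: 0.3%, 2.3%, 5.5%. Decelerating: 0.5%, 4.3%, 5.5%. Doubling yearly: 0.5%, 1.8%, 5.5%.
- Mean survival 3 years: 0.5%, 4.3%, 7.7%.
- Loss 0% or 8% per year: final figure 5.8% or 5.0%.
- Patients who entered the window as denominator: 1.5% at year 1, 5.6% at year 5, 8.0% at year 10.
- No death or loss: the final figure is about 19%.

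**On-treatment endpoint, same model.** At 0.5 per patient-year: 14% at year 1, 21% at year 5, 23% from year 6 (23/14 = 1.6-fold). At 2 per patient-year: 42%, 53%, then 56% (56/42 = 1.3-fold).

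**The case against.** Patient incidence as n and % is a usual adverse event summary, the study is purely descriptive, and nothing in Section 8.7.2.4.2 forbids a rate beside it. A statistical analysis plan that is not shown may already add one. That is fair: the statement that no rate is given holds for the protocol and is not proven for the study. But the protocol does name a measure for this endpoint, and it names person-time for others over the same windows, so this is more than detail left for later.

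Several stronger readings are tempting and are not supported:
- A reader might blame death and loss for the rise. They lower the percentage: without them it climbs further. Incomplete exposure at the data cut is the driver.
- A reader might treat all follow-up as one risk period, or expect the on-treatment endpoint to drift as much. The protocol has two windows, and the on-treatment window is short, so its percentage levels off soon after enrolment closes.
- A reader might conclude that the final percentages are wrong. Section 8.7.1.2 waits until every patient has had the opportunity for 5 years. Apart from loss and withdrawal, the percentage is then an observed cumulative incidence with death as a competing event, a legitimate quantity.
- A reader might hope that rates would make the two periods comparable. They would not, because the on-treatment endpoint counts all events and the post-treatment endpoint only those attributed to IMLYGIC.

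Two mitigations stand in part. Annual reports show total patient-years, so growing exposure is visible, though not by window. And with enrolment from 2017 and this version dated October 2022, the steepest part of the rise has probably passed.

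**Conclusion.** The point holds as a modest reporting weakness, mainly for post-treatment related adverse events and serious adverse events in the remaining annual reports. Under a constant hazard of 5 per 100 patient-years and 5-year uniform enrolment, the crude percentage goes from about 0.5% at year 1 to 3.4% at year 5 and 5.5% at the end. From year 5 on, the remaining rise is 5.5/3.4, about 1.6-fold.

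The upward direction held in every scenario tried. The size rests on an assumed hazard, enrolment length and exit pattern, none of which the protocol fixes for this endpoint. The on-treatment endpoint is affected less, and the final analysis little.

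**What to change.** In Section 8.7.2.4.2, keep n and %. Beside it, report patients with a first event per 100 patient-years at risk, with a 95% confidence interval and the patient-years shown, separately for the on-treatment and post-treatment windows. Use the windows already defined for the herpetic endpoints, stopping each patient's time at the first event of the type counted. Apply this in annual and final reports, with priority to post-treatment related adverse events and serious adverse events.

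The cost is one extra table column; the dates are already collected. The rate also has a limit: it stays level across reports only if the hazard is roughly constant within the window. If events cluster early in the window, it will fall as exposure accrues, so it should be read with n, % and the patient-years.

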8.7.2.4.3 Subgroup Analysis

The primary endpoint will be presented by variables that may relate to occurrence of primary endpoint, including:

- age
- sex
- race
- ethnicity
- history of herpetic infections (yes or no)

8.7.3 Analysis of Safety Endpoints/Outcomes

Details of the analyses of safety endpoints are outlined in Section 8.7.2.4.2.

The Medical Dictionary for Regulatory Activities (MedDRA) version 19.0 or later will be used to code all adverse events.

8.8 Quality Control

The Investigator is to maintain a list of appropriately qualified persons to whom he/she has delegated study duties. All persons authorized to make entries or corrections on eCRFs will be included on the Amgen Delegation of Authority Form. The Investigator and study staff are responsible for maintaining a comprehensive and centralized filing system of all study-related (essential) documentation, suitable for inspection at any time by representatives from Amgen or applicable regulatory authorities.

Documents to be maintained for the study are as follows:

 Patient's files containing the completed eCRF, patient identification list, and informed consent forms (ICFs), as applicable.

- Study files containing the protocol with all amendments, copies of prestudy documentation, and all correspondence to and from the Institutional Review Board (IRB)/Independent Ethics Committee (IEC).
- All source documentation supporting entries into the eCRFs must be maintained and available upon request.
- Source documents are original documents, data, and records from which the
 patient's eCRF data are obtained. These include but are not limited to hospital
 records, clinical and office charts, laboratory and pharmacy records, diaries,
 microfiches, radiographs, and correspondence.
- Retention of study documents will be governed by the contractual agreement with Amgen.
- Additional steps of quality control are:
 - The sponsor will provide protocol-specific training to all site staff; additionally, a completion guide for the eCRF will be provided.
 - Updates to eCRFs will be automatically documented through the software's "audit trail".
 - The Investigator signs only the Investigator Verification Form for this electronic data capture (EDC) study. The signature indicates that the Investigator inspected or reviewed the data on the CRF and agrees with the content.

8.9 Limitations of the Research Methods

8.9.1 Internal Validity of Study Design

Identification of the primary endpoint, incidence rate of herpetic infection with detection of talimogene laherparepvec DNA among patients enrolled in Study 20130193 may be susceptible to measurement error because suspected cases of herpetic infection in the real world may be infrequently brought to medical attention. Herpetic infection data retrieved from the study will be collected in a rigorous manner, and the patients themselves will be an important source of information. Targeted education and training linked to the Prescribing Information will ensure that patients and Investigators are aware of the signs and symptoms that may indicate herpetic infection and of the need for timely reporting for sample collection. These study procedures for identifying herpetic infection are built upon approaches for data collection within clinical studies of herpes simplex vaccine (Belshe et al, 2012), natural history studies of HSV (Mark et al, 2008; van Velzen et al, 2013), and the pharmacovigilance program for varicella vaccine in Europe and United States (Galea et al, 2008; Goulleret et al, 2010). However, unlike the study population with a grievous illness, these prior approaches were conducted in generally healthy populations. As an indicator of how well patients are reporting suspected herpetic infection, it is anticipated that study patients should report infection within the range of occurrence for the general population (ie, frequent recurrences of

Protocol Number: 20130193

Date: 12 October 2022 Page 32 of 62

oro-labial lesions are reported by 3% to 5% of the general population (Rooney et al, 1993).

8.9.2 **External Validity of Study Design**

Generalizability of study results may be limited by use of a study population based on a convenience (ie, not random) sample of study sites participating in the Postmarketing IMLYGIC Surveillance Program. Study sites that are selected will be among those with the earliest adoption of IMLYGIC. While the study patients will be recruited from these study sites, the patient inclusion and exclusion criteria are limited to best reflect any use of IMLYGIC in real-world, clinical practice. To describe if the Study 20130193 patients are representative of broader population of IMLYGIC patients, all patients in the screening log and the study patients will be reported by proportion for sex, age, and disease stage.

8.9.3 Withdrawal From Treatment, Procedures, and Study

A patient has the right to withdraw fully from the study at any time and for any reason without prejudice to his or her future medical care by the physician or the institution. Withdrawal of full consent for a study means that the patient does not wish to or is unable to continue further study participation; patient data up to withdrawal of consent will be included in the patient's study data. Any patient may withdraw consent to participate in the study at any time during the study. The Investigator will discuss with the patient appropriate procedures for withdrawal from the study.

Should a patient request or decide to withdraw from the study, all efforts will be made to complete and report the observations as thoroughly as possible up to the date of withdrawal. All information should be reported on the applicable eCRF.

Reasons for removal from protocol-specified observation might include:

- withdrawal of consent
- death
- lost to follow-up.

9. PROTECTION OF PATIENTS

9.1 **Informed Consent**

Where an informed consent is required per local regulations, an initial sample ICF is provided for the Investigator or designee to prepare the informed consent document to be used at his or her site. Updates to the sample informed consent form are to be communicated formally in writing from the Amgen Clinical Study Manager to the

Protocol Number: 20130193 Date: 12 October 2022

Investigator or designee. The written informed consent form is to be prepared in the language of the potential patient population.

Before a patient's participation in the study, the Investigator or designee will explain to the subject, or his/her legally authorized representative, the aims, methods, anticipated benefits, and potential hazards of the study, and answer all questions regarding the study.

The acquisition of informed consent is to be documented in the patient's medical records, and the ICF is to be signed and personally dated by the patient or a legally acceptable representative and by the person who conducted the informed consent discussion. The original signed ICF is to be retained in accordance with institutional policy, and a copy of the signed ICF must be provided to the patient or the patient's legally authorized representative.

If local regulations do not require an informed consent to be signed but mandate that the subject is notified about the study, the investigator or designee should document the notification process in the subject's medical record.

If a potential patient is illiterate or visually impaired, the Investigator must provide an impartial witness to read the ICF to the patient and must allow for questions. Thereafter, both the patient and the witness must sign the ICF to attest that informed consent was freely given and understood.

9.2 Institutional Review Board (IRB)/Independent Ethics Committee (IEC)

A copy of the protocol, proposed ICF, other written patient information, and any proposed advertising material must be submitted to the IRB/IEC for written approval. A copy of the written approval of the protocol and ICF must be received by Amgen before study can be executed. The Investigator must submit and, where necessary, obtain approval from the IRB/IEC for all subsequent protocol amendments and changes to the informed consent document. The Investigator is to notify the IRB/IEC of deviations from the protocol or serious adverse event(s) occurring at the site and other adverse event reports received from Amgen, in accordance with local procedures. The Investigator is responsible for obtaining annual IRB approval and IRB/IEC renewal throughout the duration of the study. Copies of the Investigator's reports, where applicable by local regulations and the IRB/IEC continuance of approval must be sent to Amgen.

Page 33 of 62

Any protocol amendments will be submitted to the local IRB for their review and approval. Annual IRB approval/renewal throughout the duration of the study will be obtained and copies of the IRB continuance of approval will be sent to Amgen.

9.3 Patient Confidentiality

The Investigator must ensure that the patient's confidentiality is maintained for documents submitted to Amgen.

- Patients are to be identified by a unique patient identification number. The key to re-identify patients must not be shared with Amgen.
- Where permitted, date of birth is to be documented and formatted in accordance with local laws and regulations.
- On the eCRFs demographics page, in addition to the unique patient identification number, include the age at the time of enrollment.
- For serious adverse events reported to Amgen, patients are to be identified by their unique patient identification number, initials (for faxed reports, in accordance with local laws and regulations), and date of birth (in accordance with local laws and regulations).
- Documents that are not for submission to Amgen (eg, signed ICFs, as applicable)
 are to be kept in confidence by the Investigator, except as described below.

In compliance with local country regulations, it is required that the Investigator and institution permit authorized representatives of the company, of the regulatory agency(s), and the IRB/IEC direct access to review the patient's original medical records for verification of study-related activities and data. Direct access includes examining, analyzing, verifying, and reproducing any records and reports that are important to the evaluation of the study. The Investigator is obligated to inform and obtain the consent of the patient to permit such individuals to have access to his/her study-related records, including personal information.

10. COLLECTION, RECORDING, AND REPORTING OF SAFETY INFORMATION AND PRODUCT COMPLAINTS

10.1 Definition of Reportable Events

10.1.1 Adverse Events

An adverse event is any untoward medical occurrence in a patient administered a pharmaceutical product(s) irrespective of a causal relationship with this treatment.

An adverse event can, therefore, be any unfavorable and unintended sign (including an abnormal laboratory finding, for example), symptom, or disease temporally associated

Amgen Proprietary - Confidential

Product: IMLYGIC®

Protocol Number: 20130193
Date: 12 October 2022
Page 35 of 62

with the use of a product(s), whether or not considered related to the product(s). The definition of an adverse event includes:

- Worsening of a pre-existing condition or underlying disease.
- Events associated with the discontinuation of the use of a product(s) (eg, appearance of new symptoms).

It is the Investigator's responsibility to evaluate whether an adverse event is related to an Amgen product prior to reporting the adverse event to Amgen.

